### **Pre-Intervention Testing (Weeks 1-2)**

**Cognitive Battery:** Participants will complete consent forms, vision screening, and cognitive tasks including assessment for episodic memory, executive function, inductive reasoning, working memory, verbal fluency, speed of processing, and crystallized intelligence. The cognitive session will last around 3 hours in total. Details of the cognitive battery participants will complete during this period can be found in Appendix A.

**Take-Home Questionnaires:** Self-reported questionnaires are completed by the participants on their own by logging into our website. Login information will be e-mailed to participants immediately following the pre-test cognitive battery. Participants may log in and out to complete the questionnaires at their own pace, but if they choose to complete all questionnaires in one sitting, it will take approximately 160 minutes in total. See Appendix A for the list and description of the questionnaires.

**Neuroimaging:** Participants who meet the MRI screening requirements will be given the option of completing the MRI battery. MRI scanning will last approximately 75 minutes and include both structural and functional scans. Details of the MRI scans can be found in Appendix A.

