### **Mid-Intervention Cognitive Behavioral Battery: (Weeks 8-9)**

Mid-way through the intervention period, participants will be asked to complete the cognitive battery again (found in full in Appendix A). This will help with statistical analysis, specifically growth curve analysis.

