*Latent Factor Modeling.* As a further form of secondary analysis, we will analyze the cognitive outcome variables simultaneously using a latent-variable approach. With this method, one models the several cognitive variables at each measurement time as being statistically independent given an unobserved, subject-specific latent variable. One accommodates serial correlation within subjects by estimating correlation of the latent variable within subjects over time. The approach evaluates treatment and time effects by modeling the mean of the latent variable as a function of the predictors, and each subject's estimated latent trajectory serves as a summary of his outcome status. We will also apply such models to the four-variate fMRI primary outcome.

*Neuroimaging Analyses.* We will test for a Group x Time interaction on the primary measure of modulation capacity. For the large-scale brain network analyses, we will utilize measures of connectivity between major nodes within the networks as indicators to develop constructs for the executive fronto-parietal network, salience network, and default network at each interval of data collection. To measure increases in hippocampal volume, we will segment the left and right hippocampus into four regions of interest (subiculum, CA1 and CA2/CA3/CA4, dentate gyrus, and entorhinal cortex) for all individual high-resolution MRI images. This division into 4 regions of interest (ROI) will ensure sufficient reliability and reproducibility of the subfield distinctions. These ROIs will be entered into the same Group x Time ANOVA as in the fMRI analyses.

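### The secondary latent-variable model names no test-specific correlation across visits; if such stability exists it misfits, overstates the latent correlation and in some settings loses power

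*Combined protocol and SAP*

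**What the plan says.** The SAP, under Analyses of Secondary Outcomes (Latent Factor Modeling), introduces the method so: "As a further form of secondary analysis, we will analyze the cognitive outcome variables simultaneously using a latent-variable approach". Its structure is that the cognitive variables at each visit are taken to be "statistically independent given an unobserved, subject-specific latent variable". For correlation between visits it says: "One accommodates serial correlation within subjects by estimating correlation of the latent variable within subjects over time". Treatment and time effects enter by "modeling the mean of the latent variable as a function of the predictors", and each subject's estimated latent trajectory serves as the outcome summary. The same kind of model is to be applied to the four-region fMRI outcome.

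The SAP names no subject-by-test effect, same-test residual correlation, fit check or robust standard error for this model.

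The protocol repeats the measurements. For weeks 1-2: "Details of the cognitive battery participants will complete during this period can be found in Appendix A". For weeks 8-9: "participants will be asked to complete the cognitive battery again". Cognitive testing is repeated in weeks 15-16. Imaging is done before and after the intervention only, in eligible volunteers.

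**The concern.** Someone who is good at one particular test, say story recall, tends to be good at it at every visit, beyond what general memory ability predicts. With only the latent variable correlated over time, the model implies that a test correlates with itself across visits no more than equally loaded tests correlate with each other. Test-specific stability then has nowhere to go except into the latent correlation.

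Three things are at stake. The latent trajectory, used as each subject's summary, looks more stable than it is. The tests may be weighted inefficiently. Model-based standard errors may be too large, so that a real effect is missed. With 30 subjects per arm, avoidable loss of precision matters.

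**Working it through.** **Inputs.** From the documents: 90 subjects, 30 per arm; three cognitive visits; two imaging visits; four fMRI regions; 5 episodic memory tests and 22 cognitive tests in all (5 + 5 + 3 + 4 + 5 across the constructs in Appendix A). The documents give no power, effect size, SD or alpha for this analysis, so there is no stated figure to reproduce. Assumed: unit test variance, loadings λ, latent correlation ρ, a share s of each test's residual variance that is stable across visits, two-sided alpha of 5%, and 80% power for the correct model. Data are taken as complete, two arms are compared, and the effect is a common shift in the latent mean at post-test.

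**Step 1: misfit.** With m equal tests, the true correlation across visits is λ²ρ between different tests and λ²ρ + s(1 − λ²) for the same test. The model without test-specific terms fits one value to both, so the latent correlation becomes

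ρ_fit = ρ + s(1 − λ²)/(mλ²), capped at 1.

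- m = 5, λ² = 0.5, ρ = 0.80, s = 0.5: 0.80 + 0.25/2.5 = **0.90**. True correlations are 0.65 (same test) and 0.40 (different tests); the model gives 0.5 × 0.90 = 0.45 for both.
- λ = 0.55 (λ² = 0.3025), other inputs the same: 0.80 + 0.34875/1.5125 = 1.03, so the estimate sits at 1.
- m = 22, λ² = 0.5: 0.80 + 0.25/11 = 0.82.
- Four regions, λ² = 0.5: 0.80 + 0.25/2 = 0.925.

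With 5 tests and loadings 0.71, the expected likelihood-ratio misfit at n = 90 is 0 at s = 0, about 88 at s = 0.3, about 250 at s = 0.5 and 552-576 at s = 0.7.

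**Step 2: the treatment test.** The model was fitted to the true covariance by minimum Kullback-Leibler distance. This gives the SE that the model reports (SE_m), the true SE of its estimate (SE_t) and the SE of the correct model (SE_c). The effect is δ = (1.96 + 0.84) × SE_c, power is Φ((δ − 1.96 SE_m)/SE_t), and type I error is 2Φ(−1.96 SE_m/SE_t). With 5 tests, 3 visits and arms sharing a baseline mean:

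| Loadings | Stable share s | ρ | ρ_fit | SE_c | SE_m | SE_t | Type I | Power | Power, robust SE |
|---|---|---|---|---|---|---|---|---|---|
| 0.5-0.8 | 0.5 | 0.80 | 0.91 | 0.190 | 0.190 | 0.190 | 5.0% | 80% | 80% |
| 0.71 | 0.7 | 0.90 | 1.00 | 0.141 | 0.155 | 0.141 | 3.2% | 74% | 80% |
| 0.71 | 0.5 | 0.95 | 1.00 | 0.137 | 0.154 | 0.137 | 2.8% | 72% | 80% |
| 0.71 | 0.7 | 0.95 | 1.00 | 0.118 | 0.152 | 0.119 | 1.3% | 61% | 79% |
| 0.5-0.8 | unequal, mean 0.54 | 0.80 | 0.91 | 0.188 | 0.191 | 0.192 | 5.1% | 79% | 78% |
| 0.5-0.8 | unequal, mean 0.54 | 0.95 | 1.00 | 0.138 | 0.163 | 0.145 | 2.8% | 68% | 76% |

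Fourth row by hand: δ = 2.80 × 0.118 = 0.330; (0.330 − 1.96 × 0.152)/0.119 = 0.27; Φ(0.27) = 0.61.

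**Step 3: two sources of loss.**

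- *Latent correlation at its bound.* Below 1, with equal shares, the inflated latent correlation absorbs the omitted term and the SE is right. At 1 it cannot, and SE_m is too large (0.152/0.119 = 1.28 in the fourth row). Low loadings reach the bound sooner. With loadings 0.55 and the effect taken as a time-by-treatment contrast with baseline free, ρ = 0.8 gives an SE 3% too large, 4.4% type I error and 78% power at s = 0.5. At s = 0.7 it gives 15%, 2.5% and 71%.
- *Unequal stable shares.* The tests are weighted badly, which a robust SE does not repair. With shares from 0.1 to 0.9, loadings 0.71 and ρ = 0.8, variance is about 12% larger than needed: Φ(2.80/√1.12 − 1.96) = Φ(0.69) = 0.75. Settings with widely unequal tests gave about 7-13%. The milder spread in the fifth row gives (0.192/0.188)² = 1.04.

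**Step 4: more tests.** With 22 tests, equal loadings 0.71, s of 0.5-0.7 and ρ of 0.7-0.95, there is no loss. With unequal loadings and shares, power is 75-79%.

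**The case against.** Five objections have force.

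- **Wording.** A reader might infer that the plan sends all serial correlation through the latent variable and rules out anything else. It does not say so. The text is a generic sketch, the independence is stated within a visit, and same-test correlation across visits is left unmentioned rather than excluded. This stands. What remains is that one route is named, and a programmer following the text would fit only that one.
- **Size.** A reader might infer a fixed loss of power. Every driver (λ, ρ, s, the number of tests, the 80% reference) is assumed, and the SAP does not say how many tests enter. Similar tests with moderate loadings, or many tests, lose nothing. The ranges are not bounds in the other direction either: at loadings 0.55 and s = 0.7, power runs 79%, 71%, 57% and 45% as ρ goes from 0.7 through 0.8 and 0.9 to 0.95.
- **Consequence.** The analysis is secondary and the errors are conservative. The primary ANCOVA or mixed model on the scalar composite does not use this model. This stands.
- **Imaging.** Scans are done twice, not three times, in a subset of unstated size. The mechanism carries over, as the 0.925 in step 1 shows, but no power figure is claimed for it.
- **Cost.** One variance per test could mean 22 extra parameters at n = 90, with up to 15% to 20% dropout expected. This is a fair limit on the fix, and robust standard errors alone recover most of the loss at the bound. They do not cure the misfit, the overstated latent correlation or the poor weighting.

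**Conclusion.** The point holds as a minor improvement to a secondary analysis. If the stable share is above zero, which is likely for the same tests repeated within 16 weeks but is not quantified in the documents, the model as described misfits and overstates the latent correlation (0.80 becomes 0.90 in the worked case).

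The effect on the treatment test ranges from none, to about 7-13% extra variance when stable shares differ widely, to power of roughly 60-78% against 80% when loadings are low or the latent trait is very stable, and lower still when both apply. Type I error is at most 5.2% in the tabulated runs and their companions, and close to 5% or below elsewhere. These results assume complete data and a common treatment shift on the latent variable.

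A reader might infer that the trial's main conclusions, or its false-positive rate, are at risk. The documents do not support that: the primary analysis is separate, and the error runs toward missing an effect.

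**What to change.** In the SAP's Latent Factor Modeling text, add a subject-by-test random effect: y_ijt = μ_jt + λ_j η_it + u_ij + e_ijt for subject i, test j and visit t, with u_ij independent of η_it. Residuals for the same test with a common correlation across visits are equivalent. Add a subject-by-region effect to the fMRI version. List which tests enter, and report robust standard errors, with a small-sample correction for the imaging subset.

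The cost is SAP wording and one extra variance parameter per test or region; no new data are needed. If many tests are entered at n = 90, a common-variance constraint may be required. It keeps the model estimable but gives back part of the gain when stable shares really differ between tests. If the stable share is near zero, the added terms should be estimated near zero and little is lost.
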